4.7.2 Additional aspects to disease evolution

The international consensus response criteria define both progressive disease and loss of response (see Appendix G).

A study of brentuximab vedotin (SGN-35) in CD30-positive systemic mastocytosis with or without an associated hematological clonal non-mast cell lineage disease (AHNMD)

4.8 Safety assessments

Safety assessments will consist of evaluating all adverse events and serious adverse events, laboratory parameters including hematology and chemistry, vital signs, physical examinations, and documentation of all concomitant medications and/or therapies.

4.8.1 Laboratory evaluations

All evaluations must be performed according to the Visit Schedule and Assessment (Table 2). When abnormal laboratory values or test results constitute an adverse event (ie, induces clinical signs/symptoms or requires therapy) they must be recorded on the Adverse Events CRF.

All laboratory values must be drawn and assessed PRIOR to administration of SGN-35 on the day of its administration. Baseline laboratory values need not be repeated if performed within 72 hours of the initial dose of SGN-35.

Vital signs and Physical Examination

A physical examination and vital signs must be performed at baseline, and the beginning of each cycle, and at the end of treatment (EOT), or progressive disease, whichever comes first, and at time of loss of response (LOR). Vital signs and physical exams will also occur on day +30 after EOT which will be end of study visit in non-responders; in responders—vital signs and physical examination will occur every six weeks after completion of 8 cycles of therapy until week 48, then every 12 weeks.

More frequent exams may be performed as clinically indicated. Vital signs include heart rate, blood pressure, and body temperature. Height (in cms) and weight (in kgs) will be captured at baseline and weight (in kgs) will be captured at the beginning of each cycle. ECOG status will be recorded at these visits.

Information about the physical examination must be present in the source documentation at the study site. Significant findings present prior to the start of study drug must be included in the Relevant Medical History/Current Medical Conditions CRF. Significant findings made after the start of study drug that meets the definition of an adverse event must be recorded on the CRF.

Performance Status

The ECOG Performance Status Scale will be used in this study (Appendix A).

Hematology

Hematology will include total white blood cell count with differential (neutrophil count lymphocyte, monocyte, eosinophil, basophil, mast cell, blast count, and immature granulocytes), hemoglobin, hematocrit, platelet count and reticulocyte count (% and absolute). Hematology labs are required at screening, on day 1 of each cycle during cycles 1 to 8 , day 8 and 15 of cycle 1, day 10 of cycles 2 to 8, at end of treatment (EOT), or time of progressive disease (whichever comes first), and/or at time of loss of response (LOR). Hematology will also be drawn on day +30 after EOT in non-responders; in responders—hematology will be drawn every six weeks after completion of 8 cycles of therapy until week 48, then every 12

A study of brentuximab vedotin (SGN-35) in CD30-positive systemic mastocytosis with or without an associated hematological clonal non-mast cell lineage disease (AHNMD)

weeks. For cycles 9-16, end of treatment cycle 16 and end of study, hematology labs should be repeated exactly as cycle 1-8.

Blood chemistry

Biochemistry includes sodium, potassium, chloride, bicarbonate, BUN, creatinine, glucose, calcium, total and direct bilirubin, albumin, alkaline phosphatase, SGOT and SGPT, LDH, and uric acid, (phosphorus will be additionally done on cycle 1 day 1, cycle 1 day 3 and cycle 1 day 8 only, for complete evaluation of tumor lysis), amylase, and lipase. Blood chemistry labs are required at screening, on day 1 of each cycle during cycles 1 to 8, day 3 of cycle 1 (for complete evaluation of tumor lysis), day 8 of cycle 1, day 15 of cycle 1, at the end of treatment - (EOT) or at time of progressive disease (whichever comes first), and/or at time of loss of response (LOR). Blood chemistry will also be drawn on day +30 after EOT in non-responders; in responders, blood chemistry will be drawn every six weeks after completion of 8 cycles of therapy until week 48, then every 12 weeks. For cycles 9-16, end of treatment cycle 16 and end of study, chemistry labs should be repeated exactly as cycle 1-8. Phosphorus is not to be repeated after cycle 1 day 8.

Coagulation

Coagulation includes PT/INR and PTT. These labs are required on screening, day 1 of each cycle during cycles 1 to 8, and at the end of treatment (EOT) after cycle 8, or progressive disease, whichever comes first. PT/INR and PTT are NOT required for re-staging, at cycles 9-16, end of treatment cycle 16 and end of study.

Serum Tryptase Level

Serum tryptase levels are obtained at screening, day 1 of each cycle, at the end of treatment (EOT), or at time of progressive disease (whichever comes first), and/or at time of loss of response (LOR). Serum tryptase will also be drawn on day +30 after EOT in non-responders; in responders, serum tryptase level will be drawn every six weeks after completion of 8 cycles of therapy until week 48, then every 12 weeks. **If the serum tryptase assay sensitivity does not permit recording of specific values above 200 ng/ml, the sample should be diluted to obtain a specific serum tryptase value rather than a non-specific value of ">200 ng/ml".** For cycles 9-16, end of treatment cycle 16 and end of study, serum tryptase should be repeated exactly as cycle 1-8.

Pregnancy Test

A pregnancy test will be obtained relevant patients during screening, day 1, and on day 1 of each treatment cycle for cycles 1- 8 (patients who need re-treatment will undergo pregnancy testing during re-staging and during potential re-treatment cycles ie, cycles 9-16). Pregnancy test will be done at the end of cycle 8 (end of treatment) and if re-staged, end of treatment cycle 16 and end of study (30 day follow up) visit.

Chest X-Ray (2 views- PA and Lateral)

A chest-x-ray (2 views-PA and lateral) will be performed at screening. If findings considered disease-related are found on chest x-ray at screening (eg, pleural effusion), then a chest x-ray(2 views-PA and lateral) will be performed at the end of cycles 4 and 8 or EOT, whichever comes first, and at the time of progressive disease or loss of response (LOR). A chest X-ray (2 views-PA and lateral) will also be done if patient is assessed for re-staging to get additional

A study of brentuximab vedotin (SGN-35) in CD30-positive systemic mastocytosis with or without an associated hematological clonal non-mast cell lineage disease (AHNMD)

8 cycles of treatment. Interval chest x-rays can be performed at the discretion of the investigator.

Electrocardiogram

An ECG must be performed within 28 days prior to Day 1.

MRI (or CT) Abdomen / Pelvis with and without contrast including 3D spleen and liver volumes

An MRI Abdomen/Pelvis with and without contrast including 3-D spleen and liver volumes (CT with and without contrast including 3-D spleen and liver volumes may be used instead) must be performed within 28 days prior to Day 1 and repeated at the end of cycle 4, and at the end of cycle 8 or EOT, whichever comes first, and at the time of progressive disease. Interval CT scans can be performed at the discretion of the investigator. Repeat MRI (or CT) abdomen/pelvis with and without contrast including 3D spleen and liver volumes will be performed at time of Loss of Response (LOR) through the re-staging studies and repeated during re-treatment cycles 9-16 on a schedule identical to cycles 1 and 2-8.

If patients are removed from study before the end of cycle 4, an MRI (or CT) abdomen / pelvis with and without contrast including 3D spleen and liver volumes should be performed at completion/discontinuation if feasible.

After completion of 8 cycles, a repeat MRI or CT abdomen/pelvis with and without contrast including 3D spleen and liver volumes should be performed at the end of week 48 and every 6 months thereafter in ongoing responders.

Myeloproliferative Neoplasm Symptom Assessment Form (MPN-SAF) Modified for Mast Cell Symptoms (Appendix F)

The MPN-SAF modified for mast cell symptoms will be completed by the patient at screening, day 1 of the trial, day 1 of each cycle through 8 cycles, end of study, and for ongoing responders, every 6 weeks at the time of their maintenance visits through week 48, then every 12 weeks thereafter. The MPN-SAF modified for mast cell symptoms will also be filled out at time of progressive disease or loss of response (LOR). It will also be completed during re-treatment cycles (cycles 9-16) according to the schedule outlined in cycle 1 and 2-8.

Visits, Laboratory Studies and Procedures at Time of Loss of Response (LOR)

At the time of protocol-defined loss of response (LOR) after completion of 8 cycles of therapy, patients will undergo all screening labs (except for PT and PTT and 12-lead EKG) to re-stage disease before re-initiation of SGN-35 for up to an additional 8 cycles (eg, cycles 9-16). For re-treatment during cycles 9-16, the schedule of laboratory studies, exams, and procedures will be identical to cycles 1 and 2-8, with an end of treatment (EOT) visit at the completion of cycle 16 of therapy except PT and PTT which will not be performed with cycles 9-16, end of treatment (EOT) visit at the completion of cycle 16 or end of study.

4.9 Central Histopathology Review

Central histopathology review will be performed in University of New Mexico. This will include review of peripheral blood smear (results of CBC should also be submitted), bone marrow aspirate, bone marrow core biopsy and review of any biopsied tissue with mast cell involvement. The time points for collection of bone marrow aspirate and biopsy material includes the following:

1. Pre-trial (screening); see note in protocol (section 3.3.1) regarding the use of material within 3 months prior to signing study consent:

If some histopathologic studies for mast cell disease were performed within 3 months prior to signing the consent, such material can be used in place of or to complement histopathologic studies for screening after discussion between Drs. [name], [name], and [name] to ensure sufficient quality and quantity of sample for central histopathologic review and testing. However, any histopathologic studies that were not performed should be undertaken during the screening.

2. End of cycle 4
3. End of cycle 8, or at the EOT, whichever comes first
4. At the time of loss of response (LOR) or progressive disease. For patients with LOR, marrows will be performed during the re-staging period and repeated during re-treatment cycles 9-16 on a schedule identical to cycles 1 and 2-8.
5. After completion of 8 cycles, for ongoing responders, a repeat bone marrow aspirate and biopsy should be performed at the end of week 48 and every 6 months thereafter.

Peripheral blood smears and bone marrow aspirates should be unstained or stained with a Wright Giemsa stain. Biopsy slides will be stained with Hematoxylin-Eosin stain. Special stains (ie, reticulin, etc.) and immunohistochemical stains (ie, CD117, tryptase, and CD25, and CD30) will be performed on representative paraffin blocks from biopsies of tissues with mast cell disease (or unstained slides if blocks cannot be provided). Flow cytometry immunophenotyping will be performed on bone marrow (ideal) or peripheral blood (if mast cell leukemia present) for analysis of mast cell phenotype which includes CD117, CD25, CD2, and CD30.

Each institution will perform a *KIT* D816V mutation from bone marrow aspirate (if aspirate not available, then core biopsy material). Institutions may obtain *KIT* mutation status from peripheral blood.

The following are requested by [name] at University of New Mexico for central histopathology review which must be completed before formal drug treatment is started (eg, day 1 infusion). This information will also be provided separately in a lab manual appendix:

1-2 peripheral blood smears (unstained preferred)

1-3 bone marrow aspirate smears (unstained preferred)

A study of brentuximab vedotin (SGN-35) in CD30-positive systemic mastocytosis with or without an associated hematological clonal non-mast cell lineage disease (AHNMD)

8-10 unstained bone marrow biopsy slides

1 heparinized (green top) tube of bone marrow aspirate (3 ml minimum) for flow cytometry

5 Notable laboratory value criteria, special methods and scales

Performance status scale: ECOG.

Adverse event scale: NCI CTC version 4.03.

6 Data Handling and Record Keeping

6.1 Case Report Forms

Investigator is responsible for entering the information required by the protocol into the Case Report Forms (paper or electronic, that uses validated software and conforms to FDA requirements for electronic data capture). If using electronic Case Report Forms, during system failures data is captured on paper and is later transferred to electronic Case Report Forms. The Investigator must certify that the data are complete and accurate by applying an electronic signature to the electronic Case Report Form and later receives a CD-ROM or paper copies of the patient data for archiving at the investigational site.

All data requested on the CRF must be recorded. All missing data must be explained.

6.2 Source Documents

Source data is all information, original records of clinical findings, observations, or other activities in a clinical trial necessary for the reconstruction and evaluation of the trial. Source data are contained in source documents. Examples of these original documents, and data records include: hospital records, clinical and office charts, laboratory notes, memoranda, subjects' diaries or evaluation checklists, pharmacy dispensing records, recorded data from automated instruments, copies or transcriptions certified after verification as being accurate and complete, microfiches, photographic negatives, microfilm or magnetic media, x-rays, subject files, and records kept at the pharmacy, at the laboratories, and at medico-technical departments involved in the clinical trial.

6.3 Records Retention

It is the investigator's responsibility to retain study essential documents for at least 2 years after the last approval of a marketing application in their country and until there are no pending or contemplated marketing applications in their country or at least 2 years have elapsed since the formal discontinuation of clinical development of the investigational product. These documents should be retained for a longer period if required by an agreement

A study of brentuximab vedotin (SGN-35) in CD30-positive systemic mastocytosis with or without an associated hematological clonal non-mast cell lineage disease (AHNMD)

with Seattle Genetics. In such an instance, it is the responsibility of the lead investigator (the study sponsor) to inform other investigators/institutions as to when these documents no longer need to be retained.

6.4 Confidentiality

Information about study subjects will be kept confidential and managed according to the requirements of the Health Insurance Portability and Accountability Act (HIPAA). Those regulations require a signed subject authorization informing the subject of the following:

- What protected health information (PHI) will be collected from subjects in this study
- Who will have access to that information and why
- Who will use or disclose that information
- The rights of a research subject to revoke their authorization for use of their PHI.

In the event that a subject revokes authorization to collect or use PHI, the investigator, by regulation, retains the ability to use all information collected prior to the revocation of subject authorization. For subjects that have revoked authorization to collect or use PHI, attempts should be made to obtain permission to collect at least vital status (ie, that the subject is alive) at the end of their scheduled study period.

7 Statistical methods

7.1 Populations

Two populations will be considered for the evaluation of this study:

1. The primary efficacy population includes all patients who have received at least 1 dose of SGN-35.
2. The safety population includes all patients in the study who received at least one dose of SGN-35. The safety population will be used for all safety analyses.

7.2 Background and demographic characteristics

Qualitative background variables (sex, race, stage of disease, etc.) will be summarized using contingency tables. Appropriate descriptive statistics will be used to summarize quantitative background variables (age, weight, etc.). All demographic and disease related data will be listed in detail.

7.3 Study medication

The dosage of SGN-35 of each patient will be listed. In addition, descriptive statistics will be used to summarize the duration of exposure of the study medication, the number of patients by the maximum number of doses received, and the number of patients who experienced dose reduction by duration of exposure. The reasons for dose change of the study medication will also be listed.

7.4 Concomitant therapy

Concomitant medications and significant non-drug therapies prior to and after the start of the study medication will be summarized by dose level according to the Anatomical-Therapeutic Chemical (ATC) classes.

7.5 Primary Objective- Efficacy evaluation

The efficacy of the regimen will be assessed in this study. The primary efficacy endpoint is response rate. A responder is an ASM or mast cell leukemia patient (with or without an AHNMD) who experiences a complete or partial remission, or clinical improvement per international consensus response criteria. Patients with stable disease (SD) or progressive disease (SD) are considered non-responders (NR). Patients with missing tumor assessment or who die or discontinue the study before having their first assessment will be considered non-responders. Best clinical response will be tabulated. The rate of complete remission, partial remission, and clinical improvement (CI) will be estimated and its 95% confidence interval will be provided.

7.6 Secondary Objectives

7.6.1 Safety evaluation

The assessment of safety will be based on the frequency of adverse events and on the number of laboratory values that fall outside of pre-determined ranges. Other safety data will be considered as appropriate.

Adverse events will be summarized by presenting the number and percentage of patients having any adverse event, having an adverse event in each body system and having each individual adverse event. Any other information collected (eg, severity or relatedness to study medication) will be listed as appropriate.

Laboratory data will be summarized by presenting shift tables using extended normal ranges (baseline to most extreme post-baseline value), by presenting summary statistics of raw data and change from baseline values (means, medians, standard deviations, ranges) and by the flagging of notable values in data listings.

Data from other tests will be listed, notable values will be flagged, and any other information collected will be listed as appropriate. Any statistical tests performed to explore the data will be used only to highlight any interesting comparisons that may warrant further consideration.

A study of brentuximab vedotin (SGN-35) in CD30-positive systemic mastocytosis with or without an associated hematological clonal non-mast cell lineage disease (AHNMD)

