2.3.3 Secondary Safety Endpoints

- Type, incidence, severity, seriousness, and relatedness of adverse events
- Laboratory abnormalities

3. Investigational Plan

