3.3.2 Inclusion and exclusion criteria

Inclusion criteria

- Aged ≥ 18 years of age
- Patient must give written informed consent
- ECOG performance status of 0-3 (Appendix A)
- Life expectancy > 12 weeks
- Meeting the following laboratory values:
 - AST and ALT ≤ 2.5 x Upper Limit of Normal (ULN) (Exception: ≤ 5 x ULN, if elevation is considered related to ASM/MCL)
 - Serum direct bilirubin ≤ 1.5 x ULN; if considered related to ASM/MCL ≤ 3 x ULN
 - Serum creatinine ≤ 2.0 mg/dL
 - Creatinine clearance (CrCl) ≥ 30 mL/min
- A diagnosis of SM per 2008 WHO Criteria (see Appendix B)
- Neoplastic mast cells must express CD30 by immunohistochemistry or flow cytometry (histopathologic determination made centrally by [name])
- Patients with ASM and MCL (diagnostic criteria in Appendix C) with or without an AHNMD are required to have at least one of the eligible organ damage findings as defined by the international consensus response criteria
- Both females of childbearing potential and males who have partners of childbearing potential must agree to use an effective contraceptive method during the study and for 30 days following the last dose of study drug.
- Females of childbearing potential must have a negative serum or urine B-hCG pregnancy test result within 7 days prior to the first dose of SGN-35. Females of non-childbearing

potential are those who are postmenopausal greater than 1 year or who have had a bilateral tubal ligation or hysterectomy.

Exclusion criteria

- Patients unwilling or unable to comply with the protocol.
- Any other concurrent severe known disease (except carcinoma in-situ) concurrent severe and/or uncontrolled medical condition (eg, uncontrolled diabetes, or active uncontrolled infection) which could compromise participation in the study.
- History of another primary malignancy that has not been in remission for at least 3 years. (The following are exempt from the 3-year limit: non-melanoma skin cancer, fully excised melanoma in situ [Stage 0], curatively treated localized prostate cancer, and cervical carcinoma in situ on biopsy or a squamous intraepithelial lesion on PAP smear.)
- Patients with cardiovascular disease including congestive heart failure Grade 3 or 4 according to the NYHA classification, left ventricular ejection fraction of < 50%, myocardial infarction within previous 6 months and poorly controlled hypertension.
- Women who are pregnant or lactating.
- Patients with \geq Grade 2 neuropathy

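### Section 7.6.1 plans no per-patient table by CTC grade or relatedness, so a laboratory value already abnormal at entry can worsen markedly without showing as a shift

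*Combined protocol and SAP*

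**What the plan says.** Section 7.6.1 (Safety evaluation) opens by resting safety on the frequency of adverse events and "on the number of laboratory values that fall outside of pre-determined ranges". It then specifies three laboratory displays:

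- shift tables: "by presenting shift tables using extended normal ranges (baseline to most extreme post-baseline value");
- descriptive summaries: "by presenting summary statistics of raw data and change from baseline values (means, medians, standard deviations, ranges");
- listings: "by the flagging of notable values in data listings".

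Adverse events are tabulated as the number and percentage of patients with any event, with an event in each body system, and with each individual event. For the rest: "Any other information collected (eg, severity or relatedness to study medication) will be listed as appropriate". Section 2.3.3 nevertheless gives the first safety endpoint as "Type, incidence, severity, seriousness, and relatedness of adverse events".

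Neither the extended nor the pre-determined ranges are defined. Section 5, whose title promises criteria for notable laboratory values, contains only the ECOG scale and "Adverse event scale: NCI CTC version 4.03".

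Under Section 3.3.2, patients are "required to have at least one of the eligible organ damage findings" in the consensus response criteria (Appendix G).

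**The concern.** A shift table with low, normal and high categories is informative when most patients start in the normal category. In this trial many will not, because the entry criteria select for organ damage that is often measured by a blood test. A patient who starts low and falls much further stays in the same cell.

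Safety and tolerability is the first secondary objective (Section 2.2). Section 1.2 reports Grade 3 neutropenia in 13% and Grade 4 in 7% of patients in the earlier phase 2 lymphoma studies. In advanced mastocytosis the question is how often the drug makes existing organ damage or cytopenia worse, and by how much. If no table counts patients by grade and relatedness, a reader of the report must rebuild that figure from listings, and two of the named endpoints are never summarised.

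**Working it through.** The plan states no figure for laboratory safety, so there is none to reproduce. The Simon design figures in Section 7.8 are not involved.

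**1. How many entry routes are laboratory-based.** Appendix G has nine organ-damage rows. Seven rest on laboratory or transfusion values: liver tests, albumin, neutrophils, anemia (two rows) and thrombocytopenia (two rows). Two do not: ascites/pleural effusion and symptomatic splenomegaly. So 7 of 9 rows are laboratory-based, but one finding suffices and a patient can qualify without any of the seven.

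**2. What a range-based shift table shows.** Take an illustrative baseline platelet count of 70 x10^9/L, which meets the Appendix G entry level of Grade 2 or worse (below 75), and a worst value of 20. Classify a value as low if it is below the lower limit L. The plan does not give L, so it is varied:

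| Assumed L (x10^9/L) | Baseline 70 | Worst 20 | Table shows |
|---|---|---|---|
| 75, 100, 125 or 150 | low | low | no shift |
| 25 or 50 | normal | low | shift |
| 20 | normal | normal | no shift |

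In general the fall is hidden if L is above 70 or is 20 or less, and visible if L lies above 20 and up to 70. Hemoglobin behaves the same way: an illustrative fall from 9.5 to 6 g/dL is low to low for L of 10, 11 or 12.

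**3. What the other laboratory displays show.** Suppose one patient has that fall of 50 and the others are unchanged.

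- Mean change with 11 patients: -50/11 = -4.5. With 26 patients: -50/26 = -1.9.
- Median change: 0 in both cases.
- Minimum change: -50.

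Only the range reveals the fall. It gives neither the number of patients affected nor the grade or relatedness. The flags depend on notable-value criteria that are not stated.

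**4. What the protocol's own rules need.** Table 1 in Section 4.2.5 says that, for patients with Grade 2 to 3 cytopenia at baseline, only Grade 4 cytopenia suspected to be drug-related counts as hematologic toxicity. That requires baseline grade, worst grade and relatedness. The study-hold rule in Section 4.2.5 counts patients with emergent, drug-related, non-hematologic Grade 3 or 4 toxicity (4 of 11). No table in 7.6.1 yields either number.

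**5. Counting values rather than patients.** From the hematology schedule in Section 4.8.1, a patient completing eight cycles has 1 (screening) + 8 (Day 1 of each cycle) + 2 (cycle 1 Days 8 and 15) + 7 (Day 10 of cycles 2 to 8) + 1 (end of treatment) = 19 scheduled draws. A patient stopping after cycle 2 Day 10 has 1 + 2 + 2 + 1 = 6, or 7 with an end-of-treatment draw. Removing the two pre-dose draws (screening and cycle 1 Day 1) leaves 17 against 5, a ratio of 3.4. A count of out-of-range values, if produced, would weight completers about three to one for reasons unrelated to toxicity.

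**The case against.** The best defence is that the shift table is only one of several displays. Section 7.6.1 also plans change-from-baseline summaries and flagged listings. In a first stage of 11 patients, a reader can go through listings patient by patient. Laboratory worsening can also become an adverse event: Section 8.1 counts worsening of a preexisting condition, and laboratory abnormalities that need active management or suggest organ toxicity. The planned event tables would then count it once per patient. All of this stands, so a reader who infers that laboratory worsening would be lost, or that laboratory safety rests on range counts and shift tables alone, goes beyond the documents. It does not close the gap. The event tables carry no grade or relatedness, and Sections 4.8.1 and 8.1 differ on when a laboratory value becomes an adverse event.

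Four other stronger readings also fail.

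- That the shift table hides worsening whatever limits are used: some limits would show it (step 2).
- That every patient enters with an abnormal laboratory value: the two non-laboratory rows can qualify alone, and masking affects only parameters abnormal at baseline. New neutropenia from a normal baseline would show as a shift. The neutrophil row itself starts at Grade 3, so a Grade 2 to Grade 4 example does not apply to that row.
- That cytopenias feed the study-hold rule, or that the rule waits for these tables: it is limited to non-hematologic toxicity, and nothing ties it to Section 7.6.1.
- That a table of value counts is planned: the wording appears only in the opening sentence, and no specified display is of that kind. Step 5 is therefore a caution about an unspecified summary.

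**Conclusion.** The concern holds in a limited form. Section 7.6.1 uses undefined ranges for laboratory shifts and plans no table by CTC grade or relatedness, although severity and relatedness are named endpoints and the protocol's toxicity rules are written in those terms. For a parameter out of range at baseline, marked worsening can therefore leave the shift table unchanged. No other planned summary gives the number of patients affected by grade.

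The size depends on two unknowns: the range limits, and how many patients enter with each parameter abnormal. The platelet example assumes ungraded low/normal/high categories and a lower limit of 75 or above. The underlying information would be collected and would appear in listings, so this is a weakness of summary and reporting and not a loss of data. It does not touch the primary endpoint, the sample size or the two-stage decision rule. It should be corrected because the better method is standard and inexpensive.

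**What to change.** In Section 7.6.1:

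- Add, for each gradable laboratory parameter, a per-patient shift table of baseline CTC 4.03 grade against worst on-treatment grade. State the on-treatment window (for example, first dose to 30 days after the last dose, matching the adverse event reporting period in Section 8.1) and how re-treatment cycles are handled.
- Tabulate treatment-emergent adverse events (onset or worsening on or after the first dose) by maximum grade and by relatedness, one count per patient, with related Grade 3-4 events shown separately for hematologic and non-hematologic toxicity.
- Express any out-of-range summary as a number of patients, not of values, and define every extended, pre-determined or notable range that is kept.
- Keep the change-from-baseline summaries and flagged listings. They still show deterioration within a grade, including in patients who start at the highest laboratory grade.
- Reconcile Sections 4.8.1 and 8.1 on when a laboratory value is recorded as an adverse event.

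The cost is revised wording and a little more programming. CTC 4.03 is already the trial's scale, and the laboratory values, severity and relatedness are already to be collected. No visit, sample size or error rate changes.
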